## 6.6 Enrollment Criteria

### At screening visit:

#### 6.6.1 Screening Inclusion Criteria

1. Age 18 years or older
2. Body Mass Index (BMI)  $\leq 35 \text{ kg/m}^2$
3. Diagnosis of symptomatic osteoarthritic joint in the index joint (Kellgren- Lawrence grade I to III) to be treated with MONOVISC injection.
4. Failed conservative treatment for joint osteoarthritis.
5. NRS pain on walking  $\geq 4$  and  $\leq 9$  in the index joint.
- 6.
7. Subject must be willing to abstain from other treatments of the index joint for the duration of the study.
8. Subject is willing to discontinue all analgesics including NSAIDs, except acetaminophen/paracetamol, at least seven days before the treatment injection and through the completion of the study.
9. Subject is willing to use only acetaminophen/paracetamol (up to a maximum of 4.0 grams per day per the package insert) for the treatment of joint pain for the duration of the study. At least forty-eight hours prior to the Baseline Visit and each follow-up assessment, the subject is willing to discontinue use of acetaminophen/paracetamol.
10. Subject is willing to maintain a stable dose of oral glucosamine and/or chondroitin sulfate products throughout the study, if taken prior to signing the informed consent form (ICF).
11. Able and willing to provide signed informed consent.

#### 6.6.2 Screening Exclusion Criteria

1. History of hypersensitivity to any of the ingredients in the hyaluronan
2. Infection or skin disease in the area of the injection site or index joint
3. NRS pain on walking  $> 3$  in the contralateral joint
4. NRS pain on walking  $> 3$  in the ipsilateral knee or hip joints.
5. Subject received an injection of Hyaluronic Acid (HA) and/or steroid in either joint within 6 months of signing the informed consent form (ICF). A subject will be excluded if they are planning to receive an HA or steroid injection (other than the study injection) in either joint during the course of this study.
6. Known inflammatory or autoimmune disorders (including rheumatoid arthritis, gout), or other pre-existing medical conditions that, in the opinion of the investigator, could impact treatment of the index joint or affect the ability of the subject to accurately complete the study questionnaires and comply with the study requirements.
7. Subject is taking medications at the time of signing the ICF which could interfere with the treatment procedure, healing and/or assessments. This includes but is not limited to oral or injectable anticoagulant treatments, anti-aggregant platelet treatment, chronic opioid analgesics. Low dose aspirin used for cardiovascular protection is allowed if a stable regimen is maintained for the duration of the study.
8. Subjects who had an oral, intramuscular, intravenous, rectal suppository or topical (excluded in index joint only) corticosteroid within 30 days of signing the ICF are excluded. Topical corticosteroid use at any site other than the index joint is allowed.

9. Significant trauma to the index ankle within 26 weeks of screening
10. Chronic use of narcotics or cannabis.
11. Ligament instability or tear in index joint.
12. Chronic impingement in the index joint requiring surgical treatment
13. Diagnosis of fibromyalgia
14. Diagnosis of osteonecrosis in index joint
15. Subject has significant varus or valgus deformity greater than 10 degrees in either knee.
16. Subject requires consistent use of an assistive device (e.g. wheelchair, walker, etc.)  
Occasional use of a cane is acceptable.
17. Uncontrolled diabetes with a HbA1c of >7%.
18. Subject is a woman who is pregnant or breastfeeding at the Screening Visit or a woman of child bearing potential who refuses to use effective contraception during the course of the study.
19. Subject is receiving or in litigation for worker's compensation.
20. Otherwise determined by the investigator to be medically unsuitable for participation in this study.

**At baseline visit****6.6.3 Baseline Inclusion Criteria**

1. NRS pain on walking  $\geq 4$  and  $\leq 9$

**6.6.4 Baseline Exclusion Criteria**

1. Subject has a decrease of  $\geq 2$  in the NRS pain on walking from Screening to Baseline in the index joint.
2. Subject has a contraindication to continue with the study treatment injection based on the visual appearance of the synovial fluid aspirate.

## 7. STUDY PROCEDURES

### 7.1 Schedule of Events

Assessments	Screening Visit Day -14 to -7 ±2 days	Baseline Visit Day 0	Month 1 Visit	Month 3 Visit	Month 6 Visit
			±3 days	± 7 days	± 7 days
Informed Consent	X				
Evaluation of Enrollment Criteria	X	X			
Demographics	X				
Vital Signs	X				
History Joint OA (Index & Contralateral for hip, knee and ankle)	X				
Medical History	X				
Concomitant Medication	X	X	X	X	X
Assess non-drug therapies	X	X	X	X	X
Adverse Event Assessment		X	X	X	X
Collect & Review Subject Diary		X	X	X	X
Rescue Medication usage / washout		X	X	X	X
Patient Global Assessment (PGA)	X	X	X	X	X
AOFAS index for index and contralateral ankle	X	X	X	X	X
Index and Contralateral Joints Pain (0-10 Numeric Rating Scale) for Hip, Knee and Ankle joints	X	X	X	X	X
Physical Evaluation of Index and Contralateral Joints for Hip, Knee and Ankle joints	X	X	X	X	X
Study Injection		X			
Dispense Subject Diary		X			

## **7.2 Procedure Description**

### **7.3 Screening Visit (Day -14 to -2 days)**

The following screening and eligibility data will be collected.

#### **7.3.1 Informed Consent Form**

The subject must sign the Informed Consent Form (ICF) prior to enrollment or undergoing study treatment.

#### **7.3.2 Inclusion / Exclusion Criteria**

Confirm subject eligibility against the inclusion and exclusion criteria.

#### **7.3.3 Demographics**

The following demographic information will be collected at the Screening Visit:

- Age
- Gender
- Race
- Height
- Weight
- Index joint – left / right
- Index / Contralateral Joint OA Grades for Hip, Knee and Ankle

#### **7.3.4 Vital Signs**

Patient will have vital signs assessed.

- Blood pressure
- Pulse
- Temperature

#### **7.3.5 History of Joint Osteoarthritis**

Subject's history of osteoarthritis including prior treatments for both index and contralateral hip, knee and ankle joints.

#### **7.3.6 Medical History**

The relevant medical history of the index and contralateral hip, knee and ankle joints will include, but is not limited to, an assessment of:

- History of trauma in the joints
- History of surgery in the joints
- History of injections to treat pain in the joints
- History of other treatments in the joints including failed prior treatments including but not limited to corticosteroid injection, HA injection, acupuncture, RICE (Rest, Ice, Compression, Elevation), NSAIDS.

### 7.3.7 Pain Assessment

Patient reported Pain on walking of the index and contralateral hip, knee and ankle joints will be measured with a Numerical Rating Scale (NRS).

### 7.3.8 Physical Evaluation of Index & Contralateral Joints

The Investigator will perform the physical evaluation of the index and contralateral hip, knee and ankle joints at the time points included in Schedule of Events, and will include the following assessments:

- Appearance of redness or swelling
- Assessment of pain upon palpation of the joints
- Assessment of comorbidities at the joints

### 7.3.9 Medications

Medications that the subject may have been taking prior to study enrollment for conditions unrelated to the treatment of osteoarthritis, other than analgesics including NSAIDs, may be continued as long as they will not interfere with study assessments. Low dose aspirin (81 mg) used for cardiovascular protection is allowed if a stable regimen is maintained for the duration of the study.

#### 7.3.9.1 Restricted Medications

All analgesics other than acetaminophen/paracetamol are prohibited during the study. This includes, but is not restricted to, NSAIDs, opioids and topical agents for treatment of osteoarthritis of index joint. Topical corticosteroids are allowed at any other site other than the index joint. The analgesic medication use will be monitored at each subject assessment through review of the subject diary.

#### 7.3.9.2 Rescue Medications

Acetaminophen/paracetamol (up to a maximum of 4.0 grams per day per the package insert or as per regional limitations) will be allowed as the rescue medication for the treatment of Osteoarthritis for the duration of the study. At least forty-eight hours prior to the Baseline Visit, 1, 3 and 6 Month Assessments the subject should discontinue use of the rescue medication.

The subject should be instructed to track pill usage daily to convey accurate pill counts at follow-up assessments.

#### 7.3.9.3 Concomitant Medications

A medication is considered concomitant if taken after signing the ICF and up to and including the last follow-up assessment. Data on medications will include: medication name, dose, unit, route, frequency, start date, stop date, indication and whether the medication was taken for an AE.

At each study assessment, the subject will be asked about any new medications that were started since the last assessment. Indications for any new medications started after the study treatment will be recorded as AEs, unless the medications are administered for a pre-existing condition.

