### 6.4 Safety Endpoint:

The incidence, severity, and relationship to treatment of all Adverse Events (AE) will be collected from the treatment injection to the 6 month assessment.

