## 8. ADVERSE EVENTS

### 8.1 Reporting

#### 8.1.1 Adverse Events

All AEs that occur during or after injection will be recorded. Worsening of a condition that existed prior to the study injection should be recorded as an AE. At each assessment during the trial, AEs that have occurred since the previous assessment must be recorded. All subjects will be questioned and evaluated for AEs or complications associated with the procedure. Complications of the injection include, but are not necessarily limited to: pain, swelling, erythema, bleeding and/or infection at the injection site. The Investigator will determine the severity and relationship of each event, as defined above.

AEs observed during the course of this study, regardless of severity or relationship to the injection will be recorded on the CRF. Each reported complication/AE will also include the duration, action taken to address the AE, and the resolution status (e.g. ongoing, resolved). These subjects will continue to be evaluated for safety at all scheduled follow-up points.

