### **9.2.2 Adverse Events**

Subjects with AEs will be summarized with frequencies and percentages by system organ class and preferred term, severity, and relationship to investigational product/procedure. In summaries of AEs by severity and relationship to investigational product/procedure, subjects reporting multiple episodes will be counted once under the worst severity and the strongest relationship, respectively. Serious Adverse Events will also be presented by relationship to investigational product/procedure.

Adverse events occurring prior to the index treatment will not be recorded in this trial.

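### Section 7.3.9.3 makes the indication of a new post-injection medicine an adverse event even when its use is purely preventive, so overall AE incidence can be inflated

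*Protocol*

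**What the plan says.** Section 7.3.9.3 of the protocol governs concomitant medication. For each medicine the site records, among other items, "indication and whether the medication was taken for an AE". At every assessment "the subject will be asked about any new medications that were started since the last assessment". The rule at issue follows: "Indications for any new medications started after the study treatment will be recorded as AEs, unless the medications are administered for a pre-existing condition".

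Three other places determine what happens to such an entry:

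- Section 8.1.1: "AEs observed during the course of this study, regardless of severity or relationship to the injection will be recorded on the CRF".
- Section 6.4, on the endpoint used for safety: "The incidence, severity, and relationship to treatment of all Adverse Events (AE) will be collected from the treatment injection to the 6 month assessment".
- Section 9.2.2, the summary: "Subjects with AEs will be summarized with frequencies and percentages by system organ class and preferred term, severity, and relationship" to the product or procedure.

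Section 13.2 requires investigators to carry out the protocol's instructions to the letter. The synopsis names safety, with clinical improvement, as the study objective, and plans 25 subjects in one open-label group.

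**The concern.** The rule covers every new medicine and exempts only treatment of a condition that was already there. A vaccine or travel prophylaxis falls outside that exemption, because no condition, old or new, is being treated. It is still a new medicine with an indication, so the sentence as written calls for an AE. The site would then have to give a severity and a relationship to something that did not happen to the patient, and the subject would enter the AE tables.

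What is at stake is how the overall AE percentage reads. There is no control group in which the same artefact would appear, and the group is small enough for a few such entries to be visible in the headline figure. Up to 20 sites are planned. A site that follows the wording and a site that applies ordinary AE judgement could report different rates from similar patients.

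**Working it through.** **Step 1: is the rule limited anywhere else?**

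- *AE definition.* Section 8.1.1 says: "The Investigator will determine the severity and relationship of each event, as defined above". The available protocol text contains no preceding definition of an AE that would exclude preventive use.
- *Relationship.* Section 8.1.1 records AEs whatever their relationship to the injection, so rating an entry unrelated does not remove it.
- *Medication field.* The item on whether a medicine was taken for an AE shows that other uses are foreseen, but the next paragraph of 7.3.9.3 names only one, the pre-existing condition. For a vaccine, a site could properly answer no in that field and still be told to record an AE.
- *Discretion.* Section 13.2 leaves none.

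So nothing in the protocol narrows the rule for preventive use.

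**Step 2: size per subject.** The protocol gives no AE rate and no rate of new preventive medication, so it has no figure on this point to reproduce. The only input it supplies is the planned size of 25 (synopsis). One subject counted solely for a preventive medicine adds 1/25 = 4 percentage points. This is approximate, because section 6.5 gives 25 as a maximum and section 9.1 as a minimum.

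**Step 3: illustration of the total, on assumed inputs.** Let p be the true share of subjects with at least one AE, and q the share who start a new preventive medicine during follow-up. If the two are independent and every such use is recorded as an AE:

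reported incidence = 1 − (1 − p)(1 − q) = p + (1 − p)q

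For p = 20%:

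- q = 0%: 0.20 + 0.80 × 0 = 20% (5 of 25 subjects)
- q = 10%: 0.20 + 0.80 × 0.10 = 28% (7 of 25)
- q = 20%: 0.20 + 0.80 × 0.20 = 36% (9 of 25)
- q = 30%: 0.20 + 0.80 × 0.30 = 44% (11 of 25)

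The same formula for other assumed values of p:

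| True incidence p | q = 0% | q = 5% | q = 10% | q = 20% | q = 30% |
|---|---|---|---|---|---|
| 10% | 10% | 14.5% | 19% | 28% | 37% |
| 20% | 20% | 24% | 28% | 36% | 44% |
| 40% | 40% | 43% | 46% | 52% | 58% |

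The excess is (1 − p)q. It shrinks in proportion if only some sites apply the rule literally. With p and q both 20%, a fully literal site would expect 36% and a site using ordinary judgement 20%.

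**The case against.** The strongest reply is that the sentence is meant as a prompt for finding unreported AEs. It follows the question about new medicines, and its contrast with a pre-existing condition suggests that an indication here means a condition under treatment. Section 8.1.1 asks for duration, action taken and resolution, which do not fit a vaccination. This is a fair account of the probable intent, but the wording does not say it and section 13.2 asks for literal compliance.

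A second reply is that controls exist: review of CRF instructions and AE procedures before enrolment (section 12), data queries (10.2), and sponsor instructions on uniform assessment (13.16). They may catch stray entries, but none of them changes the rule being trained and checked.

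Three stronger readings are tempting, and the documents do not support them:

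- *That AE incidence is in fact inflated.* It can be. If no subject starts a preventive medicine, the inflation is zero, and the protocol gives no rate from which to say otherwise.
- *That the contraception requirement generates AEs.* The exclusion of "a woman of child bearing potential who refuses to use effective contraception during the course of the study" is a screening criterion, so contraception would ordinarily be in use before the injection and would not be new.
- *That medication around planned procedures is a clear case.* Such procedures will often be for a pre-existing condition, which the exception arguably covers.

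It also stands that no hypothesis test or numerical threshold in the protocol uses overall AE incidence, and that the tables by preferred term would make such entries visible.

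**Conclusion.** The point holds as a drafting defect of low weight. Followed as written, section 7.3.9.3 produces AE entries for preventive use where nothing untoward occurred, so the overall AE incidence can be too high and can vary with how literally a site reads the rule.

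The only size that follows from the protocol is about 4 percentage points per affected subject. The 20% to 44% range rests on three assumptions: a true incidence of 20%, between 0% and 30% of subjects starting a preventive medicine independently of AEs, and literal application at every site. It illustrates sensitivity and is not an estimate.

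The effect would fall mainly on the overall percentage and on events rated mild or unrelated. Treatment-related AEs and SAEs, which bear most on the residual risk that section 6.5 sets out to evaluate, should barely change. The primary efficacy analysis is not affected.

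**What to change.** Reword the last sentence of section 7.3.9.3. For each new medicine started after the injection, the site checks whether it was given for a new or worsened sign, symptom or condition; if so, that condition is recorded as an AE. A medicine given with no such condition, for example for prevention, is recorded as concomitant medication only, and the existing field on whether it was taken for an AE is answered no. The exception for pre-existing conditions can stay, provided that worsening is still recorded as section 8.1.1 requires.

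The cost is one sentence in the protocol and a matching line in the CRF guidance, with no new data item. The prompt keeps its value for finding unreported events. The downside is a small reliance on site judgement about whether a condition lies behind the prescription.

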#### 7.3.9.4 Non-Drug Therapies

Non-drug therapies are any therapies used to treat the index joint that are not a pharmaceutical

treatments.

**7.3.9.5 Joint Function Assessment**

Subjects will receive assessment of the respective joints for functional use.

**7.3.9.6 Subject Diary**

Subjects will receive diary for to record rescue medications and concomitant medications.

#### **7.4 Baseline Visit: Treatment Visit (Day 0)**

The Baseline Visit (Day 0) will occur 7 to 14 days after the Screening Visit to allow for rescue medication washout. The injection will occur at this Baseline visit along with the following activities:

##### **Before Treatment Injection**

- Concomitant Medications
- Current non-drug therapies
- Confirm Medication Washout
  - If subject did not complete medications washout, reschedule the visit to allow washout to be completed.
- Patient Global Assessment (PGA)
- AOFAS index
- Index & Contralateral Hip, Knee and Ankle Joint Pain on Walking (NRS Scale)
  - Confirm the Baseline Inclusion & Exclusion criteria for NRS Pain on Walking
- Physical Exam of Index and Contralateral Hip, Knee and Ankle Joints

##### **Treatment Procedure**

The Treating Physician will always perform the Study Injection to the index joint as standard of care dictates.

Intra-articular injection of the ankle joint should be conducted under fluoroscopic or ultrasound guidance. Guidelines for the injection procedural steps are provided below. Modifications to this technique should be recorded in the CRFs.

- Patient is supine.
- Prep the skin at injection site with 1% betadine solution or equivalent.
- Peri-articular injection site anesthesia of lidocaine or topical refrigerant anesthetic (e.g. ethyl chloride) may be utilized.
- The ankle is dorsiflexed to a neutral position. Injection site is located in the anteromedial portal of the ankle joint as described for ankle arthroscopy
- Fluoroscopic or ultrasound guidance may be utilized if required to insert 18-22 gauge needle. Traction can be applied if required to gain access.
- Insert needle until resistance against the articular surface and then withdraw the needle 1-2 mm.
- If using fluoroscopic guidance, a small amount of fluoroscopic contrast agent (0.5 to 1.0 ml) should be injected through the needle to verify intra-articular placement.
- If using ultrasound guidance, a small volume of air (up to 0.5 ml) may be injected to verify IA

positioning.

- If pooling of the contrast agent or air around the needle tip is observed, the needle should be repositioned.
- When contrast agent or air is successfully injected into the joint, intra-articular placement is confirmed.
- Following confirmation of intra-articular needle placement, the joint may be aspirated to remove synovial fluid.
  - Confirm the Baseline Exclusion for synovial aspirate.
- 2 ml of MONOVISC is injected into the joint.
- Intra-articular anesthetic should NOT be administered as part of the injection procedure.
- Following the injection, the patient should be advised to maintain a low level of physical activity for the next 48 hours. Cold therapy and/or acetaminophen/ paracetamol may be prescribed to address short term injection site pain.

### **Post-Treatment Assessments and Instructions**

Prior to leaving the clinic, the subject should be evaluated for local and non-local AEs. All post-treatment signs and symptoms that are unexpected should be recorded as AEs. The expected appearance of the index joint should be discussed with the subject with a request that all unexpected symptoms be reported to a member of the study team.

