#### 4.2 Risks

Any intra-articular injection poses potential risks. However, subjects should incur no additional risks compared to injections of other frequently injected products, such as corticosteroids or diagnostic contrast agents.

Adverse events associated with single intra-articular knee injections of MONOVISC can be found in the MONOVISC Instructions for Use. These events are expected to be similar for ankle injections. In the clinical trial for MONOVISC in knee OA, adverse events that were related to the injection treatment were:

- injection site pain/swelling
- joint stiffness / swelling / effusion
- arthralgia,
- pain in extremity
- synovitis

- contusion
- subcutaneous nodule
- Baker's cyst

Adverse events not related to the index joint for MONOVISC were:

- arthralgia
- headache
- pain in extremity
- upper respiratory tract infection
- back pain

Other risks associated with intra-articular ankle injections, regardless of treatment, include:

- temporary injection site pain, swelling or tenderness
- temporary stiffness of the ankle
- malfunction of the syringe and/or needle

In rare instances, side effects could include:

- an allergic reaction to the fluoroscopic imaging contrast agent. Symptoms could include redness or inflammation at the injection site or inside the ankle joint, hives or itching.
- an allergic reaction to the local anesthetic (lidocaine). Symptoms could include redness or inflammation at the injection site or inside the ankle joint, hives or itching.
- injection site infection
- neurovascular, cartilage, or bone damage resulting from the injection itself

Finally, there is a low risk associated with radiation from the X-ray evaluation required for inclusion in the study. There is also a low risk from the radiation during fluoroscopy-guided injections

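### Section 7.4 limits Day 0 adverse event recording to unexpected signs, while Sections 6.4 and 8.1.1 require all adverse events, so anticipated local reactions may be recorded at some sites and not at others

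*Protocol*

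**What the plan says.** Three parts of the protocol set the rule for recording adverse events from the injection onward.

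- **Section 7.4, Post-Treatment Assessments and Instructions.** The subject is first evaluated for local and non-local adverse events before leaving the clinic. Then: "All post-treatment signs and symptoms that are unexpected should be recorded as AEs". Staff explain how the joint is expected to look, with "a request that all unexpected symptoms be reported to a member of the study team".
- **Section 6.4.** The safety endpoint reads as follows: "The incidence, severity, and relationship to treatment of all Adverse Events (AE) will be collected from the treatment injection to the 6 month assessment".
- **Section 8.1.1, Adverse Events.** "All AEs that occur during or after injection will be recorded", and "AEs observed during the course of this study, regardless of severity or relationship to the injection will be recorded on the CRF". The section also states: "Complications of the injection include, but are not necessarily limited to: pain, swelling, erythema, bleeding and/or infection at the injection site". For later visits it adds: "At each assessment during the trial, AEs that have occurred since the previous assessment must be recorded".

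The protocol presents mild local reactions as foreseeable. Section 4.2 lists "temporary injection site pain, swelling or tenderness" among the risks of any ankle injection and expects the knee-trial events, which include injection-site pain and swelling, to be similar in the ankle. Section 5.3 warns of passing pain or swelling. The treatment procedure in 7.4 makes provision for short-term pain at the injection site.

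**The concern.** Section 7.4 makes recording depend on whether a sign was expected. Sections 6.4 and 8.1.1 do not. The events caught between the two wordings are local reactions to the injection, which the protocol itself describes as foreseeable. A site applying 7.4 as written has the protocol's own support for calling them expected and leaving them off the record on Day 0.

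Section 6.5 gives the evaluation of the residual risk of these injections as the purpose of the study. Section 9.2.2 reports the share of subjects with each type of event, also by severity and by relationship to product or procedure. If sites read 7.4 differently, the reported incidence of related local events could be too low, uneven across up to 20 sites, or both. No statistical analysis plan can correct this, because an event that was never entered cannot be recovered in the analysis.

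**Working it through.** The point is textual and the protocol states no figure to reproduce. The check compares the rules for one case: a subject with mild, anticipated injection-site swelling seen before leaving the clinic on Day 0.

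| Question | Section 7.4 | Sections 6.4 and 8.1.1 |
|---|---|---|
| Which events are recorded? | Signs and symptoms that are unexpected | All adverse events from the injection onward |
| Any filter? | Expectedness | None by severity or relationship |
| How is anticipated local swelling treated? | Not covered by the recording sentence | Named as a complication |
| What is the subject asked to report? | Unexpected symptoms | Subjects are questioned and evaluated for events or complications |

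**Is the word a filter?** If 7.4 meant all events, the qualifier would do no work. The next sentence repeats it, after staff have described the expected appearance of the joint, so reading it as a filter is reasonable. The protocol text does not define the term for recording purposes.

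**Do other provisions recover the event?**

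1. *Later visits.* Section 8.1.1 requires recording of events since the previous assessment. After Day 0 the next scheduled visit is Month 1 (Sections 7.1 and 7.5). A brief reaction then depends on recall about a month later, by a subject who was asked to report only unexpected symptoms.
2. *Diary.* Section 7.3.9.6 issues it for rescue and concomitant medications. An untreated reaction leaves no entry.
3. *New-medication rule.* Section 7.3.9.3 turns the indication for a new post-treatment medication into an adverse event, unless the condition is pre-existing. It does not reach a reaction that is untreated or managed only with cold therapy. Where paracetamol is newly started for injection-site pain, this rule makes the pain an adverse event although 7.4 may treat it as expected.
4. *Non-drug therapies and pill counts.* These are reviewed at visits (Sections 7.3.9.2, 7.3.9.4 and 7.6) and may prompt a question, but they set no recording rule.
5. *Training and general duties.* Section 12 (review of reporting with site staff), Section 13.6 (investigator reports all adverse events) and Section 13.16 (instructions on uniform documentation) help. None says which wording applies to an anticipated Day 0 reaction.

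**Scale.** With n = 25 treated subjects (Synopsis), one subject whose reaction goes unrecorded changes that reaction's reported incidence by 1/n = 1/25 = 0.04, or 4 percentage points. The proportion with *any* related event falls by the same 4 points only if that subject has no other related event recorded, because each subject is counted once. The protocol gives neither a local-reaction rate nor an unrecorded share, so the total loss cannot be calculated.

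**The case against.** The strongest reply is that 7.4 prohibits nothing. It says unexpected signs should be recorded. It does not say expected ones should not be, and its opening sentence calls for evaluation of local events without any filter. Section 8.1.1 is the dedicated reporting section. It covers events during the injection, names these very reactions, and asks for duration, action taken and resolution for each reported complication or event. Section 4.2 itself calls injection-site pain and swelling adverse events related to treatment. A careful investigator reading the whole protocol would probably record them, and the later visits, the medication rule and site training give further chances to do so.

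Much of this stands. The conflict is an ambiguity rather than a ban, and the safeguards reduce the risk. Section 7.4 also uses *expected* only for the appearance of the joint and does not point to the lists in 4.2 or 5.3, so equating the two is a reasonable inference, not something the text states. But 8.1.1 does not say that it overrides 7.4, and 7.4 is the text staff will have in front of them on the day of injection.

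It is also fair to say that the size is unknown. The 50% enrolment cap in Section 9.1 would let one site's reading govern at most 12 of 25 subjects (48%), but that does not bound the effect, because several sites may share a reading. The 4-point step is itself only arithmetic on the planned number, which Section 6.5 gives as a maximum and Section 9.1 as a minimum.

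**Conclusion.** The concern holds as an inconsistency between stated rules that should be fixed. Section 7.4 conditions Day 0 recording and subject reporting on expectedness, Sections 6.4 and 8.1.1 do not, and no provision resolves the difference for an anticipated local reaction.

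The consequence is possible, not certain: under-recorded or uneven counts of related local events, at 4 percentage points of reported incidence per affected subject if 25 are treated. This assumes only that some sites apply 7.4 literally and that the omitted reaction is not picked up later. Confidence is high that the wordings conflict; the protocol supports no estimate of how many events would be lost.

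The effect is confined to non-serious safety data. The primary pain endpoint is untouched, and so is serious event reporting under Section 8.1.2. With a single arm, no between-group comparison is biased.

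**What to change.** Rewrite two sentences in Section 7.4 so that one recording rule applies from the injection onward:

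- Replace the recording sentence with wording such as: *Every adverse event arising during or following the injection is to be documented as Section 8.1.1 requires; this includes anticipated local reactions, for example pain, swelling or erythema at the injection site.*
- Replace the request to subjects with one to tell the study team about any new or worsened symptom, whether or not it was anticipated.

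The rule needs no expectedness field. Cover the clarification in the adverse event review already planned with site staff under Section 12.

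The cost is small. If the protocol has already been approved, Section 13.3 requires a signed amendment submitted to the competent authority and ethics committee. The change itself asks for no new data item, but the case report form is not in the protocol, so its wording should be checked. Sites will record somewhat more minor events, and the reported adverse event rate may look less favourable.
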